In populations with such extensive food shortages and severe malnutrition, relief organizations must supply emergency food in order to prevent widespread mortality. In order to initiate such life-saving interventions, relief workers must carry out assessments to determine the specific needs in each population. However, the relief food provided to emergency-affected populations is often deficient in many important micronutrients, such as iron, vitamin A, B vitamins, and others. As a result, although a relief operation may provide sufficient protein, energy, and fats, many individuals in the recipient population may manifest symptoms and signs of micronutrient deficiencies.

Both the initial assessment of an emergency-affected population and evaluation of existing food and nutrition programs require reliable data about the prevalence and severity of proteinenergy and micronutrient malnutrition. Such data are usually gathered by population-based surveys. This protocol describes the activities which are commonly included in such assessment surveys.

Intended and potential use of the findings

As stated above, organizations providing aid to emergency-affected populations need data on the type, prevalence, and severity of nutritional deficiencies in order to plan nutritional interventions. For example, the type of feeding programs implemented in a relief dependent population is often largely determined by the prevalence of acute protein-energy malnutrition in children less than 5 years of age. If acute protein-energy malnutrition is not very common, there may be no need for programs providing nutritional rehabilitation for individual children. If malnutrition is widespread, several different types of nutritional rehabilitation, including supplemental and therapeutic feeding, should be offered. In addition, specific programs, such as iron supplementation of pregnant women or children less than 5 years of age, should not be implemented without some indication that iron deficiency is a substantial public health problem in a specific population.

After the acute emergency period, when death rates have normalized and adequate health and public health programs are in place, nutrition assessment surveys are a valuable tool for outcome evaluation of various nutrition programs.

Study design and locations

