No sub-segment of the population will be specifically excluded from participation in nutrition assessment surveys in emergency-affected populations; however, some population subsegments may not be specifically chosen for inclusion. Women and children are at greater risk of most nutritional deficiencies; therefore, they will be targeted for most nutrition assessment surveys. Men are at substantially lower risk of many nutritional deficiencies and are therefore specifically not targeted for most nutritional assessments. One exception is the assessment of the causes of anemia. Men are often included in such surveys because they are much less susceptible to iron deficiency. Therefore, survey findings indicating that anemia is common among women and children but rare among men provide evidence that iron deficiency is a predominant cause of anemia.

Estimated number of participants

The specific sample size in each nutrition assessment survey depends on many assumptions and factors which may differ from one survey to the next. Commonly, such surveys include 200 - 700 households and all eligible members of target groups who live therein.

Sampling, including sample size and statistical power

The required sample size will be calculated separately for each assessment survey. All sample size calculations use the following assumptions:

- 1) The limit of statistical significance (alpha) = 0.05
- 2) The power (beta) = 0.8

The other assumptions required for sample size calculation will be decided based on the specific population to be assessed. These assumptions include:

- 1) Prevalence of nutritional condition of interest
- 2) Desired precision of point estimate of prevalence, cumulative prevalence, incidence, or mean.
- 3) Population size, if less than 10,000.
- 4) Design effect, if cluster sampling is planned.

The table below shows examples of nutrition conditions of interest, the assumptions used, and the sample size needed which may be used in nutrition assessment surveys in emergency-affected populations. These examples assume a population size greater than 10,000. Of course, the assumptions used and therefore the required sample sizes will differ depending on the nutrition conditions and specific population to be assessed.

Target group and type of malnutrition	Assumed current value	Precision required	DEFF assumed	Sample size needed
Children 6-59 months				
Wasting (< -2 SD)	20%	" 5%	2	492
Stunting (< -2 SD)	50%	" 10%	2	193

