At least one health worker on each survey team is trained to collect the biologic specimens necessary for that specific survey. Such training may include the use of the Hemocue® hemoglobinometer to measure hemoglobin concentration and use of other portable laboratory instruments to be used by survey team members in the field. Fingerstick and phlebotomy technique is reviewed and practiced on other survey team members. Although fingerstick may be taught to naïve survey team members, phlebotomy is done only by health workers already experienced in this technique. The processing and storage of specimens is also taught during the training period and closely supervised during the first days of the survey.

Data handling and analysis

Data analysis plan, including statistical methodology and planned tables and figures

The sampling methods have been previously described (see section "Sampling, including sample size and statistical power" above). Data collection procedures are described in the next section "Data collection").

In general, data analysis includes calculation of proportions to derive the prevalence of various nutrition and health conditions and mean averages of various continuous measurements. Although all possible analyses cannot be determined for all possible nutrition assessment surveys in emergency-affected populations, the example of hemoglobin will illustrate the potential types of data analysis.

An estimate of the importance of anemia among children, women, and men is generated by calculating the proportion of the survey participants for whom hemoglobin concentration falls below the WHO-recommended threshold for defining anemia (see section "Case definitions" above). In addition, survey coordinators graph the distribution of hemoglobin concentrations and calculate the mean hemoglobin concentration for each of the target groups. The statistical precision of all prevalence estimates is assessed using 95% confidence limits, and the statistical significance if differences between subgroups is assessed using Chi square.

Data collection

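### The protocol says every sample size calculation uses 80% power, but every tabulated size is a confidence-interval precision calculation with no power term, and the power is mislabelled as beta

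*Protocol*

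**What the plan says.** In the Protocol, *Sampling, including sample size and statistical power*, two inputs are fixed for every survey under the lead-in "All sample size calculations use the following assumptions". They are "The limit of statistical significance (alpha) = 0.05" and "The power (beta) = 0.8".

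The survey-specific inputs follow: the assumed prevalence, "Desired precision of point estimate of prevalence, cumulative prevalence, incidence, or mean", the population size if it is below 10,000, and the design effect under cluster sampling. None of them is an alternative value or a difference to detect. The example table matches this list, with columns for assumed value, precision, DEFF and resulting size. Of its rows the text says "These examples assume a population size greater than 10,000", so no finite-population correction applies.

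Elsewhere, *Hypothesis or questions* disclaims any hypotheses set in advance. *Data analysis plan* says "The statistical precision of all prevalence estimates is assessed using 95% confidence limits" and, for comparisons, "statistical significance if differences between subgroups is assessed using Chi square". *Intended and potential use of the findings* adds that, after the acute phase, "nutrition assessment surveys are a valuable tool for outcome evaluation of various nutrition programs".

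**The concern.** Power is a property of a test of a stated difference. Here it is declared an input to all sample size calculations, yet the inputs listed beside it are those of an estimation problem. If the table was built without power, the protocol claims a design property that it does not have.

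This matters because the protocol does test differences between subgroups and does see a role for surveys in evaluating programmes. Someone who carries the 80% over from the sampling section could take a non-significant contrast as fair evidence of no difference. The document is also generic, and each new survey computes its own size from it, so each one inherits the line.

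The wording has a further slip. Beta is the type II error probability, so 0.8 is 1 − beta. Read literally, beta = 0.8 would mean 20% power.

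**Working it through.** **1. Reproducing the table.** Inputs are the table's own p, d and DEFF = 2, with z = 1.96 from alpha = 0.05 two-sided (the plan reports 95% limits). The formula is n = DEFF × z² × p(1−p)/d², with z² = 3.8415, rounded up.

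| Rows | p | d | Calculation | Result | Table |
|---|---|---|---|---|---|
| Wasting in children; low BMI in women | 0.20 | 0.05 | 2 × 3.8415 × 0.16/0.0025 | 491.7 → 492 | 492 |
| Stunting and anemia in children; anemia in women | 0.50 | 0.10 | 2 × 3.8415 × 0.25/0.01 | 192.1 → 193 | 193 |
| Anemia in men | 0.10 | 0.05 | 2 × 3.8415 × 0.09/0.0025 | 276.6 → 277 | 277 |

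All six rows match. At these sizes the 95% half-widths are 5.0, 10.0 and 5.0 points, as intended.

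**2. Whether any power calculation gives the same sizes.** The protocol states no difference to detect. Purely for this check, the precision figure is assumed to be that difference, with alpha 0.05 two-sided, 80% power and DEFF 2. Ranges cover a fall and a rise of that size, and the one-sample ranges also cover use of the null variance throughout.

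| Rows | One-sample test | Two groups, per group | Table |
|---|---|---|---|
| 20%, 5 points | 941–1,055 | 1,812–2,188 | 492 |
| 50%, 10 points | 388–392 | 776 | 193 |
| 10%, 5 points | 476–632 | 870–1,372 | 277 |

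The most lenient version, a one-sided one-sample test, still needs 735–836, 305 and 367–504. None reproduces a row. No single figure here is what the table should read, because the protocol supports no particular test or difference.

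**3. Power of the tabulated sizes for a difference equal to the precision.** This uses a two-proportion normal test, two-sided 0.05, with effective n = n/DEFF per group. Power = Φ[(|p₁−p₂| − 1.96·s₀)/s₁], where s₀ is the pooled and s₁ the unpooled standard error.

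- *20% vs 15%, two surveys of 492, DEFF 2.* Effective n = 246 each. s₀ = √(2 × 0.175 × 0.825/246) = 0.03426 and s₁ = √((0.16 + 0.1275)/246) = 0.03419. Power = Φ[(0.05 − 0.06715)/0.03419] = Φ(−0.50) ≈ 31%.
- *20% vs 15%, two halves of one survey (246 each), DEFF 2 retained.* Effective n = 123 each. s₀ = 0.04845 and s₁ = 0.04835. Power = Φ[(0.05 − 0.09496)/0.04835] = Φ(−0.93) ≈ 18%.
- *The same halves with a smaller subgroup DEFF.* Assume 30 clusters, as in the protocol's hypothetical example. Then 492/30 = 16.4 children per cluster, and DEFF 2 implies an intracluster correlation of 1/(16.4 − 1) = 0.065. A subgroup spread evenly over the clusters has 8.2 per cluster, so DEFF = 1 + 7.2 × 0.065 ≈ 1.47. Effective n = 246/1.47 ≈ 167 each, and power ≈ 22%.
- *50% vs 40%, two surveys of 193, DEFF 2.* Effective n = 96.5 each, and power ≈ 29%.

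Over all rows and both directions at DEFF 2, power is about 24–35% between two surveys and about 14–20% between two halves.

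**4. Detectable change from 20%.** With 80% power and DEFF 2, two surveys of 492 detect a rise to about 31% (11 points) or a fall to about 11% (9 points). Two halves of one survey detect a rise to about 36% (16 points) or a fall to about 8% (12 points). The answer depends on direction and on the design effect.

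**The case against.** The strongest reply is that nothing substantive is harmed. The surveys are descriptive, the sizes are right for that aim, the rows are offered as examples, and each survey does its own calculation. On this view the power line is a superfluous default and the beta label a slip, since the word power makes the meaning plain. Most of this stands. The sizes need no change, and few readers would take the line to mean 20% power. What does not stand is the appeal to examples: the sentence covers all calculations, and the general list of inputs also lacks any difference to detect.

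A reader might infer that the protocol promises 80% power for its subgroup tests and for before-and-after evaluation. The text does not support that. The analysis section names the chi-square test without mentioning power. The remark on outcome evaluation is a general statement of usefulness and plans no specific test or pairing of surveys. The risk is that the figure gets carried over.

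It is also fair to object that the subgroup power depends on the design effect. Subgroups such as sex or age bands are spread over the same clusters and would usually have a smaller design effect than the full sample, and positive within-cluster covariance between them would raise power further. That is why a range is given. Even at 22%, power is far from 80%.

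**Conclusion.** The point holds as an error of statement. The protocol attributes to all its sample size calculations a power of 0.8 that enters none of those shown, gives no comparison for it to describe, and labels it with the wrong symbol. This follows from the document's own table and needs no outside assumption.

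The power figures show the size of the gap if the 80% were carried over to comparisons: about 31% for 20% versus 15% between two surveys of 492, and about 18–22% between two equal subgroups of one survey. They rest on a two-sided 5% normal test, on treating the stated precision as the difference of interest, and on DEFF 2 (or 1.47 for subgroups, derived from an assumed 30 clusters).

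It would be wrong to conclude that the surveys are too small. They meet their precision targets exactly.

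**What to change.** Delete the power line from the universal assumptions. In its place state that sample sizes are set for the width of a 95% confidence interval, and that no power is claimed for the subgroup chi-square tests or for comparisons between surveys.

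Add that where a particular survey is meant to detect a difference or a change, its plan names the comparison and the difference and sizes it separately, with power = 0.80 (beta = 0.20) and that survey's own design effect.

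Do not write detectable differences into the generic protocol. They change with direction and design effect, and the protocol itself cites an Afghanistan survey sized with a design effect of 1.5.

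The cost is a few sentences of protocol wording. No size in the table and no field procedure changes.

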Nutrition assessment surveys described herein will be carried out most often among displaced or emergency-affected populations. Such populations, if displaced, are sometimes settled in camps and sometimes integrated into the host community or both. Regardless of pattern of settlement, surveys will often select a sample of households and include in the survey sample all members of targeted groups who reside in those households on the day of data collection. Targeted groups may include children less than 5 years of age, women of childbearing age, school age children, adolescents, adult men, or other groups depending on the nutritional conditions to be assessed.

Case definitions

Case definitions for nutritional deficiencies commonly included in nutritional assessment surveys in emergency-affected populations are given below:

Protein-energy malnutrition in children less than 5 years of age: Undernutrition, including wasting, stunting, and underweight, in children less than 5 years of age is defined using the NCHS:CDC:WHO reference population of children. When it becomes available, the new World Health Organization (WHO) international reference population will be used instead. Children with z-scores below -2 for weight-for-height, height-for-age, or weight-for-age are defined as wasted, stunted, or underweight, respectively. Moderate wasting, stunting, and underweight are defined as a z-score less than -2 but greater than -3. Z-scores less than -3 define severe wasting, severe stunting, or severe underweight.

For children less than 5 years of age, mid-upper arm circumference (MUAC) is sometimes used to assess protein-energy malnutrition when measuring weight and height are not feasible. MUAC measurements less than 11.5 cm are classified as severely low. MUAC measurements of 11.5 - 12.4 cm are considered moderately low, and MUAC 12.5 cm or greater are considered normal.

Protein-energy malnutrition in adults: Malnutrition in adults is assessed using body mass index (BMI), which is calculated by dividing the weight in kilograms by the square of the standing height in meters. The most common cut-off points for BMI to define levels of malnutrition in nonpregnant adults are shown below.

BMI	Category of malnutrition
< 16.0	Severe
16.0 - 16.9	Moderate
17.0 - 18.4	At risk
18.5 - 24.9	Normal
25.0 - 29.9	Overweight
> 30	Obese

An alternate scheme uses both MUAC and BMI to determine the level of malnutrition according to the scheme shown below.

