Anemia (< 11.0 g/dl)	50%	" 10%	2	193
Adult women				
Malnutrition (BMI <18.5)	20%	" 5%	2	492
Anemia (< 11 g/dl)	50%	" 10%	2	193
Adult men				
Anemia (< 13 g/dl)	10%	" 5%	2	277
* DEFF = Design effect				

Of course, each assumption will be specifically formulated for each survey using existing data on that population. For example, in a recent survey in Afghanistan, prior surveys as well as qualitative data on the target population indicated that the design effect would be relatively low for most nutritional outcomes. The sample size for this survey was calculated using an assumed design effect of 1.5.

The primary objective of nutrition assessment surveys in emergency-affected populations is often to measure nutritional status of young children. Therefore, even though data are often gathered on other target household members and the household itself, the final sample size used in such surveys is often based on nutrition outcomes in young children.

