The sampling procedures used will depend on the type of data available for the population. In many displaced populations located in stable camps, an international organization, such as UNHCR, has carried out a complete or near complete census of all camp residents. This registration database supplies a complete list of all households or individuals living in the camp. In these situations, lists of households or target individuals can be generated from which to choose a sample by simple or systematic random sampling. For example, a recent anemia survey in two camps in western Tanzania assessed the prevalence of anemia in children 6-59 months of age and their mothers. It also assessed the prevalence of iron overload in adult men 30 years of age or older. In these two camps, a registration had taken place 9 months prior to the surveys, and the registration database was constantly updated to account for new arrivals and departures. As a result, the registration data provided an excellent sampling frame. Two lists were generated from the database: one of households and one of men 30 years of age or older. A systematic random sample was drawn from the household list after calculation of the required sample size. Households on the household list were visited in order to identify children 6-59 months of age and their mothers to be included in the survey. The basic sampling unit was household while the unit of analysis for nutrition variables was the individual household member. A second sample of men 30 years of age and older was selected by sysematic random sampling from the list of men. Selected men were then recruited for the survey. In this case, both the unit of sampling and unit of analysis was individual men.

In many situations, especially during acute emergencies and new settlements of displaced persons, lists of all households or individuals in the population are not available. In such cases,

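### The sizing rule reserves the design effect for cluster sampling, so list-based household surveys that analyse several members per household may fall modestly short of their planned precision

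*Protocol*

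**What the plan says.** In the Protocol, under *Sampling, including sample size and statistical power*, the fourth survey-specific sizing input is "Design effect, if cluster sampling is planned". Fixed inputs stated before it include "The limit of statistical significance (alpha) = 0.05" and "The power (beta) = 0.8". The example table that follows gives 492, 193 and 277, every row with DEFF 2.

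The same section then describes two routes to a sample. Where a camp registration list exists, households or individuals are drawn from it by simple or systematic random sampling. Where no list exists, cluster or multi-stage sampling is used. In the worked probability table a cluster is a group of households, with 20 selected in each.

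For the list-based survey in Tanzania, the section says: "The basic sampling unit was household while the unit of analysis for nutrition variables was the individual household member". In the same survey a separate sample of men aged 30 and over was drawn from a list of individuals. Under *Description and source of study population and catchment area*, the protocol states for camps and host communities alike: "surveys will often select a sample of households and include in the survey sample all members of targeted groups who reside in those households".

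**The concern.** A list-based sample of households in which every eligible member is analysed is a one-stage cluster sample with the household as the cluster. Siblings, or several women in one home, share food, income and infections, so their outcomes are likely to be positively correlated. A sample size computed at DEFF = 1 assumes independently drawn individuals. If item 4 is followed as written, a planner working from a camp register has no prompt to enter a design effect, and the survey has fewer effective observations than its stated precision implies. Because this protocol is a template for many surveys, the same optimism would recur wherever that design is used. At stake is the width of the interval around a prevalence that decides which feeding or supplementation programmes are set up.

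**Working it through.** **1. Reproduce the plan's figures.** The inputs are the prevalence p, precision d and DEFF in the example table, with z = 1.96 from alpha 0.05. The data analysis section also specifies 95% limits: "The statistical precision of all prevalence estimates is assessed using 95% confidence limits". The examples assume a population above 10,000, so there is no finite population correction.

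Formula: n = DEFF × 1.96² × p(1−p) / d², rounded up.

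| p | d | n before DEFF | n at DEFF 2 | Printed | n at DEFF 1 |
|---|---|---|---|---|---|
| 20% | ±5 | 245.85 | 492 | 492 | 246 |
| 50% | ±10 | 96.04 | 193 | 193 | 97 |
| 10% | ±5 | 138.29 | 277 | 277 | 139 |

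All three reproduce. The listed power of 0.8 is not used; including it would give 1005, 393 and 566. The last column is what item 4 yields when no design effect is entered.

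**2. Household design effect.** With m eligible members in a household and within-household correlation ρ, DEFF = 1 + (Σm²/Σm − 1) × ρ. The ratio Σm²/Σm is the size-weighted mean. The protocol gives neither m nor ρ, so both are assumptions, shown over a range:

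- 75/20/5% of households with 1/2/3 children: mean 1.3, size-weighted mean 2.0/1.3 = 1.54
- 60/30/10% with 1/2/3 children: mean 1.5, size-weighted mean 2.7/1.5 = 1.80
- 45/35/15/5% with 1/2/3/4 children: mean 1.8, size-weighted mean 4.0/1.8 = 2.22
- ρ from 0.1 to 0.5

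**3. Precision achieved at the DEFF = 1 sample size.** Half-width = 1.96 × √(DEFF × p(1−p)/n).

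| Case | DEFF | 20%, n = 246 | 50%, n = 97 |
|---|---|---|---|
| One eligible member per household | 1.00 | ±5.0 | ±9.95 |
| Low: mean 1.3, ρ = 0.1 | 1 + 0.54 × 0.1 = 1.05 | ±5.1 | ±10.2 |
| Middle: mean 1.5, ρ = 0.3 | 1 + 0.80 × 0.3 = 1.24 | ±5.6 | ±11.1 |
| High: mean 1.8, ρ = 0.5 | 1 + 1.22 × 0.5 = 1.61 | ±6.3 | ±12.6 |

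The last column applies only if a 50% outcome alone sets N at 97. If wasting at 20% ±5 sets N at 246, a 50% outcome in the same children has half-width 1.96 × √(1.24 × 0.25/246) = ±7.0 in the middle case and ±7.9 in the high case, both inside ±10.

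**4. Sample size needed to keep ±5.** 245.85 × 1.24 gives 305 in the middle case, and 245.85 × 1.61 gives about 396 in the high case, against 246.

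**The case against.** A reader might infer that surveys sized this way cannot deliver the required precision. The documents do not support that. The shortfall depends on household composition and correlation, neither of which is given. It is zero with one eligible person per household, and on a ±5 target it exceeds one point only towards the top of the assumed range.

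A reader might also infer that printed sample sizes are too small. They are not: every row carries DEFF 2, above the highest value derived here, and no list-based N is printed. That the Tanzania survey was sized at DEFF = 1 would be inference, since the protocol says only that the required size was calculated. Nor do all list-based surveys sample households; the men were drawn individually.

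The wording is also open to a kinder reading. The list of inputs is introduced as inclusive, the protocol promises to set each assumption for each survey from existing data, and a table footnote equates primary sampling units with clusters. A household drawn directly from a list is a primary sampling unit, so item 4 could be stretched to cover it. This does not clearly repair the rule, because the section otherwise contrasts cluster sampling with list-based sampling and uses cluster to mean a group of households.

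It can be added that ±5.6 instead of ±5 is within ordinary planning error. That is a fair comment on size. But error in a guessed prevalence can go either way, whereas omitting a positive household correlation always makes the stated precision too favourable.

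One could go further and claim that reported intervals will cover less than 95%. That would follow only if the planned half-width were reported as the interval, or if the analysis ignored the household. It is an analysis question, separate from the sizing rule.

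**Conclusion.** The point holds in a limited form. On its natural reading, item 4 sizes list-based household surveys at DEFF = 1. Such a survey may then fall modestly short of its planned precision whenever more than one correlated member per household is analysed. Over the assumed ranges the loss on a ±5 target runs from about 0.1 to 1.3 points, and is about 0.6 in the middle case. The larger figures for a ±10 target are confined to surveys where a 50% outcome alone fixes N, such as an anemia-only survey. These sizes rest entirely on assumed household composition and correlation; the direction rests only on several members being analysed and on positive correlation. Samples of individuals from a list, and groups with one eligible person per household, are unaffected.

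**What to change.** Reword item 4 along these lines: *Design effect, whenever the sampled unit (cluster or household) contains more than one analysed person.* For simple or systematic samples of households, estimate it as 1 + (size-weighted mean number of eligible members per household − 1) × within-household correlation. Household composition can come from the registration database and the correlation from prior surveys. Then state the precision achievable at the planned N with that design effect. Keep DEFF = 1 where individuals are drawn from a list of individuals, or where one eligible person per household is analysed.

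The change is one line of wording plus a restated precision, about ±5.6 instead of ±5 in the middle case. Restating precision accepts the wider interval and needs no further participants. A survey that must hold ±5 would instead need the larger N shown above, and that choice can be made survey by survey.
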